4 OBJECTIVES AND ENDPOINTS

Table 4-1: Objectives and Endpoints

Objectives	Endpoints
Primary 
To assess the safety and tolerability, and determine the MTD or MAAD and RP2D of BMS-986315 administered as monotherapy, and in combination with nivolumab or cetuximab, in participants with select advanced solid tumors.	
Incidence of AEs, SAEs, AEs meeting protocol-defined DLT criteria, AEs leading to discontinuation, and death.
Secondary 
To assess the preliminary anti-tumor activity of BMS-986315 as monotherapy and in combination with nivolumab or cetuximab in participants with select advanced solid tumors.To explore the PK of BMS-986315 when administered intravenously as monotherapy and in combination with nivolumab or cetuximab, in participants with select advanced solid tumors.To characterize the immunogenicity of BMS-986315 when administered alone and in combination with nivolumab or cetuximab, in participants with select advanced solid tumors.	
ORR, DOR, and PFSR at 6, 9, and 12 monthsSummary measures of PK parameters of BMS-986315 after monotherapy and combination treatment.Incidence of anti-drug antibodies to BMS-986315 when BMS-986315 is administered alone and in combination with nivolumab or cetuximab.

Table 4-1: Objectives and Endpoints

Objectives	Endpoints
Exploratory 
 To explore changes in biomarkers such as tumor inflammation, cytolytic activity, levels of intratumoral TILs (CD8), and other pharmacodynamic parameters and associations with anti-tumor activity, when BMS-986315 is administered alone and in combination with nivolumab or cetuximab. To characterize the PK and immunogenicity of nivolumab and cetuximab when administered in combination with BMS-986315. To assess the potential dose-related and exposure-related effect of BMS-986315 when administered as monotherapy, on the QTc interval. To explore OS up to 2 years following monotherapy and combination treatments. To explore impact of SARS-CoV-2 serologic status on participants with RCC, SCCHN, and NSCLC receiving BMS-986315 as monotherapy or combined with nivolumab or cetuximab in advanced solid tumors. 	
 Summary changes in biomarkers of interest eg CD8, immune-related markers and measures of association of baseline levels, and of changes in these markers with anti-tumor activity measures. Summary measure of trough nivolumab and cetuximab concentration and the incidence of anti-drug antibodies to nivolumab and cetuximab when administered in combination with BMS-986315. Summary measures of changes in QTc after monotherapy treatment from baseline by dose and association measures of QTc changes with BMS-986315 PK exposure. OSR at 1 year and up to 2 years Incidence of participants with positive SARS-CoV-2 serologic status and associations of measures of positive SARS-CoV-2 status with select safety and PD biomarkers.

Abbreviations: AE = adverse event; DOR = duration of response; DLT = dose-limiting toxicity; MAAD = maximum administered dose; MTD = maximum tolerated dose; NSCLC = non-small cell lung cancer; ORR = objective response rate; OS = overall survival; OSR = overall survival rate; PD = pharmacodynamics; PFSR = progression-free survival rate; PK = pharmacokinetics; QTc = interval corrected for heart rate using Frederica's formula; RCC = renal cell carcinoma; RP2D = recommended Phase 2 dose; SAE = serious adverse event; SARS-CoV-2 = severe acute respiratory syndrome coronavirus 2; SCCHN = squamous cell carcinoma of the head and neck; TIL = tumor-infiltrating lymphocytes.

5 STUDY DESIGN

5.1 Overall Design

This is a Phase 1/2, multicenter, open-label study of BMS-986315, administered as a single agent and in combination with nivolumab or cetuximab, in participants with select advanced solid tumors: SCCHN, RCC, and NSCLC. All participants will be evaluated for total HLA-E expression and CD8+ T cell infiltration in fresh tumor samples by immunohistochemistry (IHC).

The study is composed of 3 parts: Part 1A (dose escalation of BMS-986315 monotherapy), Part 1B (dose escalation of BMS-986315 in combination with nivolumab), and Part 1C (dose escalation of

BMS-986315 in combination with cetuximab). Each Part will have, in addition to the escalation cohorts, additional cohorts focused on studying pharmacodynamics changes associated to study treatments, called pharmacodynamics cohorts or PD cohorts. Additional tumor types and study expansion parts may be included through a protocol amendment.

Part 1A

BMS-986315 monotherapy dose escalation (Part 1A) will escalate the dose of BMS-986315 to determine the monotherapy MTD/recommended Phase 2 dose (RP2D). Specifically, Part 1A dose escalation will evaluate different doses of BMS-986315 starting at 80 mg followed by 200 mg, 600 mg, 1200 mg, and 2400 mg (flat doses, initially Q4W). If it appears that a planned dose level is associated with an unacceptable frequency of toxicities, then intermediate dose levels or an alternative administration schedule may be evaluated. Part 1A will evaluate the safety and tolerability of BMS-986315 monotherapy based on dose-limiting toxicities (DLTs), using time-to-event Bayesian optimal interval (TITE-BOIN) design to guide escalation decisions (see [Appendix 8](#) for details), and the overall assessment of available safety, PK, and pharmacodynamic data. One additional cohort of participants, the BMS-986315 monotherapy PD cohort, will be enrolled at a dose level previously cleared for safety. The PD cohort will be implemented in order to gather additional information on pharmacodynamic activity (such as tumor cytolytic activity), safety, tolerability, preliminary efficacy, and PK in a single indication, initially SCCHN participants treated with BMS-986315 monotherapy. Please refer to [Section 5.1.2.4](#) for additional information on the PD cohorts.

Part 1B

The dose escalation of BMS-986315 in combination with nivolumab (Part 1B) will evaluate the safety and tolerability of escalating doses of BMS-986315 in combination with nivolumab, to determine the combination MTD/RP2D. Treatment in Part 1B will be initiated in a staggered manner relative to the BMS-986315 Monotherapy Escalation (Part 1A). Specifically, Part 1B can be initiated upon the decision to escalate when at least 2 dose levels (the current and 1 higher) in Part 1A have been cleared for safety in accordance with dose escalation rules, after which dose escalation in Part 1A and Part 1B will proceed in parallel separated by 2 dose levels as stated above, (see [Section 7.2](#)). At no point will the dose of BMS-986315 administered in combination with nivolumab in Part 1B exceed the highest dose determined to be tolerated in Part 1A. In Part 1B, the dose of BMS-986315 will be escalated, whereas the dose of nivolumab will be fixed at 480 mg Q4W. However, if it appears that a planned dose level is associated with an unacceptable frequency of toxicities then intermediate dose levels, alternative BMS-986315 administration schedules, or lower doses of nivolumab may be evaluated.

The safety and tolerability of the BMS-986315 in combination with nivolumab will be evaluated using TITE-BOIN design, used to guide dose escalation decisions.

Additional cohorts of participants may be enrolled within up to 2 dose levels previously cleared for safety in monotherapy. These potential combination cohorts would be implemented in order to gather additional information on pharmacodynamic activity, safety, tolerability, preliminary efficacy and PK in a single indication, initially SCCHN participants treated with BMS-986315 in

combination with nivolumab. Please refer to [Section 5.1.2.4](#) for additional information on the PD cohorts.

[figure not shown]
Part 1C

The dose escalation of BMS-986315 in combination with cetuximab (Part 1C) will evaluate the safety and tolerability of escalating doses of BMS-986315 in combination with cetuximab, to determine the combination MTD/RP2D in SCCHN participants. Treatment in Part 1C will be initiated in a staggered manner relative to the BMS-986315 Monotherapy Escalation (Part 1A). Specifically, Part 1C can be initiated upon the decision to escalate when at least 2 BMS-986315 dose levels (the current and 1 higher) in Part 1A have been cleared for safety in accordance with dose escalation rules, after which, dose escalation in Part 1A and Part 1C will proceed in parallel separated by 2 dose levels as indicated above, (see [Section 7.2](#)). At no point will the dose of BMS-986315 administered in combination with cetuximab in Part 1C exceed the highest dose determined to be tolerated in Part 1A. In Part 1C, the dose of BMS-986315 will be escalated, whereas the dose of cetuximab will be fixed at 500mg/m² Q2W. However, if it appears that a planned dose level is associated with an unacceptable frequency of toxicities, then intermediate dose levels, alternative BMS-986315 administration schedules, or de-escalating doses of cetuximab may be evaluated. Specifically, if toxicity attributable solely to cetuximab is found to be in excess as compared to the known toxicity profile of the label dose of 400mg/m² followed by 250mg/m² QW, then a decision may be made to change the cetuximab dosing regimen for all of Part 1C.

The safety and tolerability of BMS-986315 in combination with cetuximab will be evaluated using TITE-BOIN design also used to guide escalation decisions. Additional cohorts of participants will be enrolled in up to 2 dose levels previously cleared for safety. The BMS-986315 in combination with cetuximab PD cohorts, will be implemented in order to gather additional information on pharmacodynamic activity, safety, tolerability, preliminary efficacy and PK in SCCHN participants treated with BMS-986315 in combination with cetuximab. Please refer to [Section 5.1.2.4](#) for additional information on the PD cohorts.

The study consists of 4 periods: Screening, Treatment, Safety Follow-up, and Survival Follow-up (up to 2 years following the EOT of study drug). The duration of the study will be approximately 4 years. The study design schematic is presented in [Figure 5.1-1](#). A detailed schematic for study period and participant flow is presented in [Figure 5.1-2](#).

Figure 5.1-1: Study Design Schematic

Abbreviations: CTX = cetuximab; MT = monotherapy; neg = negative, NSCLC = non-small cell lung cancer; PD = pharmacodynamic cohort; PD-L1 = Programmed death-ligand 1; Q2W = every 2 weeks, Q4W = every 4 weeks

^a Further expansion may be included as part of a protocol amendment

^b Dose levels will be selected based on preliminary data from dose escalation

^c The cetuximab dose may be changed to the approved dose for the entire program if excessive toxicity is observed, upon agreement between investigators and the Sponsor.

Figure 5.1-2: Study Period and Participant Flow Diagram

Abbreviation: Q4W: every 4 weeks; EOT: end of treatment

^a Alternative dosing schedule may be used

^b See [Figure 5.1-1](#) for BMS-986315, nivolumab, and cetuximab dosing schedules

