PD cohorts are included in Part 1A (one cohort) and Parts 1B and 1C (up to 2 cohorts) at different dose levels. Each of these PD cohorts will only be open once the dose level has been demonstrated to be tolerated. The objective of the PD cohorts is to obtain pharmacodynamic information, and additional data on safety, tolerability, preliminary efficacy, and PK, in participants with SCCHN. The goal of each PD cohort is to obtain approximately 10 paired biopsy samples of participants who are considered as “biomarker negative” and 20 paired biopsy samples of participants who are considered as “biomarker positive” which is consistent with the expected natural prevalence of these biomarkers in SCCHN. Therefore, up to approximately 40 participants are expected to be treated in each PD cohort in order to have 30 evaluable participants (with paired biopsies). A fresh screening tumor biopsy will be assessed for CD8 and total HLA-E using CLIA validated IHC assays.

[REDACTED]

[REDACTED]

[figure not shown]
[REDACTED]

[figure not shown]
Only those

participants who have met tissue quality thresholds and have evaluable CD8 and HLA-E can be assigned for treatment in PD cohorts. All PD cohorts will enroll participants with SCCHN. Participants treated in the PD cohorts will be administered IV doses of BMS-986315 according to the dose defined for the PD cohort (e.g., 1200 mg or 2400 mg) Q4W once per cycle, for up to 26 cycles (104 weeks) of study therapy, unless criteria for study drug discontinuation are met earlier (see [Section 8.1](#)). In Part 1B, BMS-986315 will be combined with nivolumab 480mg Q4W. In Part 1C, BMS-986315 will be combined with cetuximab 500 mg/m² Q2W.

The study consists of 4 periods: Screening, Treatment, Safety Follow-up, and Survival Follow-up (up to 2 years following the EOT of study drug). The duration of the study will be approximately 4 years. The study design schematic and participant flow schematic are presented in Figure 1 and [Figure 2](#) below.

Figure 1: Study Design Schematic

Abbreviations: CTX = cetuximab; neg = negative; pos = positive; NSCLC = non-small cell lung cancer; MT = monotherapy; PD L1 = Programmed death-ligand 1; PD = pharmacodynamic cohort; Q2W = every 2 weeks, Q4W = every 4 weeks

^a Further expansion may be included as part of a protocol amendment

^b Dose levels will be selected based on preliminary data from dose escalation

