5.1.2.2 BMS-986315 in Combination with Nivolumab Dose Escalation Design (Part 1B)

Approximately 36 participants are expected to be treated during the BMS-986315 Combination with Nivolumab Dose Escalation (Part 1B) of the study guided by TITE-BOIN for the primary objective. Additionally, up to approximately 80 participants are expected to be treated across 2 SCCHN PD cohorts in combination with nivolumab.

Based on preliminary safety, PK, and pharmacodynamic data from Part 1A, the starting dose of BMS-986315 in Part 1B may be higher than the starting dose from Part 1A. Each dose level in

Part 1B, including the starting dose, will only be opened after at least that dose and one higher dose level in Part 1A have demonstrated tolerability during the DLT observation period. Additional cohorts in Parts 1A and 1B may proceed in parallel and will be separated by at least 2 dose levels (the current and 1 higher cleared in Part 1A). Each participant will be administered IV doses of BMS-986315 (in doses based on Part 1A data) combined with 480 mg of nivolumab Q4W (once per cycle), for up to 26 cycles of study therapy (104 weeks) unless criteria for study drug discontinuation are met earlier (see [Section 8](#)).

The combination dose escalation phase (Part 1B) of the study will evaluate the safety and tolerability of BMS-986315, given in combination with nivolumab, based on DLTs, using a TITE-BOIN. During the combination dose escalation phase, approximately 3 participants will be treated at each dose level. However, to allow for any unforeseen discontinuations (such as disease progression) before the 4-week DLT period (28 days) is completed, an extra participant may be enrolled in each dose escalation cohort. Therefore, there may be a total of 4 participants (3 + 1) at the start of each cohort, provided that the fourth participant is able to start dosing within approximately 1 week of the third participant in the same dose escalation cohort. Cohort tolerability assessment and subsequent dose recommendation will occur when at least 3 evaluable participants within a cohort have completed a 4 week DLT period or have been sufficiently followed, based on the TITE-BOIN design, to make an escalation decision depending on the number of DLTs so far. Any toxicities that occur beyond the DLT period will be considered in making dose level decisions and/or dose level modifications. Additional information on DLTs can be found in [Section 5.1.3](#).

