7.2 Method of Treatment Assignment

During the screening visit, the investigative site will call into the enrollment option of the Interactive Response Technology (IRT) designated by BMS for assignment of a 5-digit participant number that will be unique across all sites. Enrolled participants, including those not dosed, will be assigned sequential participant numbers starting with 00001, (e.g., 00001, 00002, 00003....00010). The patient identification number (PID) will ultimately be comprised of the site number and participant number. For example, the first participant screened (i.e., enrolled) at site number 1, will have a PID of 0001 00001. Once it is determined that the participant meets the eligibility criteria following the screening visit, the investigative site will call the IRT to assign the participant into the open dose panel.

Participants will not be replaced if they are discontinued from the study secondary to an adverse event unless the adverse event can be determined to be unrelated to treatment. All eligible participants will be initially assigned to Part 1A (dose escalation of BMS-986315 monotherapy) until the decision is made to escalate to the third dose cohort. Subsequently, treatment in Part 1B and Part 1C can be initiated, and dose escalation in the 3 parts will occur in parallel. That is, Part 1B and Part 1C can be initiated when at least 2 dose levels (the current and 1 higher) in Part 1A have cleared the DLT period in accordance with dose escalation rules, after which dose escalation in Part 1A, Part 1B, and Part 1C will proceed in parallel. Treatment assignments will alternate between all open study parts, with consecutively treated participants assigned to different parts, through IRT, based on cohort availability and inclusion criteria.

In addition, participants enrolled in monotherapy or combination pharmacodynamic cohorts will be assigned to dose levels that are already established as safe based on data coming from the

corresponding dose escalation cohort (see [Section 5.1](#)). PD cohort enrollment will take place in Part 1A, Part 1B, and Part 1C. Within each PD cohort, participants will be further assigned to either a CD8/HLA-E positive sub-cohort (biomarker positive), or a CD8/HLA-E negative sub-cohort (biomarker negative) based on the results of biomarker expression analysis.

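### Part 1B pharmacodynamic cohorts: the Synopsis and Section 5.1 gate the dose on monotherapy clearance, Section 7.2 on the corresponding escalation cohort, and no section says which governs

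*Combined protocol and SAP*

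**What the plan says.** The opening condition for the Part 1B PD cohorts is described in several places.

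- **Synopsis (Part 1B) and Section 5.1 (Part 1B):** "Additional cohorts of participants may be enrolled within up to 2 dose levels previously cleared for safety in monotherapy". The next sentence makes clear that these are nivolumab combination cohorts.
- **Section 7.2:** participants in "monotherapy or combination pharmacodynamic cohorts will be assigned to dose levels that are already established as safe" on data from the "corresponding dose escalation cohort". The sentence cites Section 5.1.
- **Section 5.1.2.4, with the same text in the Synopsis paragraph on PD cohorts:** "Each of these PD cohorts will only be open once the dose level has been demonstrated to be tolerated". The regimen is not named.
- **Figure 5.1-1, footnote b:** "Dose levels will be selected based on preliminary data from dose escalation". Again no Part is named.
- **Part 1C sentence (Synopsis and Section 5.1):** allows PD cohorts at up to 2 levels that have already passed safety clearance, without restricting that clearance to monotherapy.
- **Section 5.1.2.2:** a Part 1B escalation level "will only be opened after at least that dose and one higher dose level in Part 1A have demonstrated tolerability".

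**The concern.** Section 5.1 names monotherapy as the source of the clearance. Section 7.2 names the matching escalation cohort. Because Section 7.2 covers monotherapy and combination PD cohorts in one sentence, the natural meaning is that each PD cohort rests on its own Part's escalation, so a Part 1B cohort rests on Part 1B data.

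The contrast with Part 1C is telling. Parts 1B and 1C are both combination Parts with the same staggering relative to Part 1A, yet only the Part 1B sentence adds the monotherapy qualifier, and no reason is given.

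At stake is the safety gate for the largest cohorts in Part 1B. A reader working from the Synopsis or Section 5.1 finds the monotherapy condition and nothing to say that combination DLT data at that dose are also needed. A reader working from Section 7.2 finds a different condition and a pointer back to Section 5.1.

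**Working it through.** **1. Cohort sizes.** Section 10.1.2 wants 30 evaluable participants per PD cohort and allows for 25% non-evaluable: 30 / (1 − 0.25) = 40, which reproduces the plan's figure. Two Part 1B cohorts give 2 × 40 = 80, and adding the 36 escalation participants gives 36 + 80 = 116, as in Section 5.2. By comparison, Section 5.1.2.2 starts a combination level with 3 to 4 participants.

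**2. Does a joint reading leave the monotherapy phrase any work to do?** Section 5.1.2.2 opens a Part 1B level only after that dose and one higher are tolerated in Part 1A. Any level cleared in Part 1B has therefore already been cleared in Part 1A. If Section 7.2 requires Part 1B clearance, the monotherapy condition is met automatically and the phrase adds nothing.

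**3. Do the cross-references settle it?** Section 7.2 points to Section 5.1, which gives the monotherapy wording. The Part 1B paragraph of Section 5.1 points to Section 5.1.2.4, which names no regimen. The provision in Section 5.1.2.2 for adding participants at a tolerated level does not mention PD cohorts. None of these resolves the difference.

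**4. Which levels fall between the two wordings?** Let k be the number of levels tolerated in Part 1A and m the number cleared in Part 1B. For simplicity, both are counted from the lowest planned dose and Part 1B is taken to start there.

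- If the Section 5.1.2.2 separation also governs PD cohorts, levels up to k − 1 can be open in Part 1B. The number meeting Section 5.1 but not Section 7.2 is (k − 1) − m.
- k = 3, m = 2: (3 − 1) − 2 = 0.
- k = 3, m = 1: (3 − 1) − 1 = 1.
- k = 5, m = 2: (5 − 1) − 2 = 2.
- Section 5.1.2 keeps the separation only until monotherapy escalation is completed. Without it the count is k − m, so k = 5, m = 2 gives 5 − 2 = 3.

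The documents do not fix m relative to k: Section 5.1.2.2 speaks of a separation of at least 2 levels. The count therefore varies. Section 5.1 itself limits PD cohorts to 2 levels.

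**5. Finished is not the same as cleared.** In Appendix 8, Table 1, a level with 2 DLTs among 3 treated leads to de-escalation without elimination; elimination at that sample size needs 3 of 3. A Part 1B level that ends with 2 of 3 has completed its evaluation, is not cleared in combination, is not eliminated, and still counts as cleared in monotherapy.

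**The case against.** The strongest reply is that there is no contradiction. Section 5.1 is permissive, while Section 7.2 is mandatory and sits in the treatment-assignment section. Following Section 7.2 also satisfies Section 5.1. On this view the monotherapy phrase merely restates the cap that Part 1B never exceeds the highest dose tolerated in Part 1A, and redundancy is not conflict. Other safeguards remain: Appendix 8 eliminates overly toxic doses from the trial, and the Safety Management Team looks for signals at least monthly.

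Much of this stands. The joint reading is available, and if Section 7.2 is followed no PD cohort opens without combination data. The dose cap and the elimination rule apply either way. But no section states the joint reading, and neither the cap nor elimination sets an opening condition, as the 2-of-3 case shows.

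The size of the problem also needs restraint. A reader might infer that 40 or 80 participants would be treated without supporting combination data. The documents do not support that: these are ceilings for optional cohorts, and no PD accrual rate is given. Purely as an illustration, the 3 per month assumed in the Appendix 8 simulations would put about 3 participants into one 28-day DLT window. That illustration covers the unfinished case only, not a level that finished without clearance.

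Nor is there evidence of a fault in the assignment system. Section 7.2 says "the investigative site will call the IRT to assign the participant into the open dose panel", and nothing shows that panels would be opened on the wrong condition.

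**Conclusion.** The point holds as an inconsistency in the wording of a safety gate that should be corrected. It rests on reading the Section 7.2 phrase as each Part's own escalation, which is the natural reading but not an explicit one.

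The affected levels are those tolerated in Part 1A whose combination DLT evaluation is unfinished, or finished without clearance. A reader might take the affected range to be exactly one level, vanishing once its evaluation ends. That does not follow: the lag between Parts is not fixed, and a completed evaluation can end without clearance. In the examples above the count runs from 0 to 3, depending on the lag and on whether the separation rule applies.

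The cohorts governed by the gate are about 40 participants each and up to about 80 of 116 in Part 1B. The number who would actually be treated under the looser wording cannot be derived from the documents, and is none if Section 7.2 is followed.

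**What to change.** Reconcile the Part 1B sentence in the Synopsis and Section 5.1 with Section 7.2, and conform Section 5.1.2.4 and the Synopsis paragraph on PD cohorts. The result should be one opening condition for Part 1B PD cohorts that names the Part whose DLT data must support it. If the Part 1B and Part 1C conditions are meant to differ, say so; if not, use the same wording for both. Which rule is right is for the sponsor and investigators to settle, and this review takes no position on it.

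The cost is a wording change in these sections. It adds no participants and leaves the sample size and the TITE-BOIN design unchanged.
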